7 RESEARCH METHODS

7.1 Study Design

This will be a long-term, observational, prospective, and voluntary participation registry-based study designed to collect and assess real-world data on participants with ALGS chronically treated with odevixibat.

The study population will comprise participants with ALGS treated with odevixibat enrolled into the registry-based study. Participants who started odevixibat treatment before the implementation of the registry-based study may also be enrolled.

As this is an observational study designed to assess real-world data, the decision to prescribe the product must be taken prior to, and independently from, the willingness of the participant to be included in the registry-based study. This decision should be made in accordance with routine/standard clinical practice. The assignment of the participant to a particular therapeutic strategy is not decided in advance by the study protocol but falls within current practice.

Participants will be treated and monitored in accordance with usual medical practice during their participation in this registry-based study. No additional assessments or tests will be required by this protocol. All relevant data collected as part of routine medical care will be captured using the electronic Case Report Form (eCRF) by the investigator and transmitted to the sponsor. If some assessments included in this protocol are not routinely performed by the investigator, the corresponding sections in the eCRF do not need to be completed.

This registry-based study will collect data at Baseline and at each Follow-up Visit. Follow-up Visits are scheduled as per routine clinical practice (expected to occur at least every 6 months or more frequently, based on the investigator's judgement).

The duration of this registry-based study is approximately 5 years. Following enrolment, participants will continue to participate in the study for ≥ 2 years or until the time point of withdrawal of consent, for up to 180 days after last dose of odevixibat (in case of treatment discontinuation), death, the end of data collection, or the sponsor decides to discontinue the study.

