7.2 Setting

7.2.1 Inclusion Criteria

To be included in the registry-based study, the participant should fulfil the following inclusion criteria:

- (1) Diagnosed with ALGS.
- (2) On (or starting) active odevixibat treatment.
- (3) Signed informed consent and assent, as appropriate. Consent/assent from the participant or legal representative should be obtained, as appropriate, before any study data collection is conducted. Participants who turn 18 years of age (or legal age per country) while participating in the study will be required to provide consent for themselves.

PAGE 23 OF 76

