- ^b End of study for participants: the last Follow-up Visit as per routine clinical practice before the planned end of data collection (Section 4), withdrawal of consent, lost-to follow up, or 180 days after treatment discontinuation, whichever comes first. In case of treatment discontinuation, the last Follow-up Visit is recommended to happen onsite approximately 180 days after last dose of odevixibat.
- ^c If the participant is < 18 years of age (or the legal age of consent in the jurisdiction in which the study is taking place), assent and parent or legally authorized representative consent will also be required. Participants who turn 18 years of age (or legal age per country) while participating in the study will be required to provide consent for themselves.
- ^d Including age, sex, date of birth (MM/YYYY), and date of ALGS diagnosis
- ^e Prior medications refer only to medications related to the treatment of ALGS, including but not limited to rifampicin, UDCA and/or other IBAT inhibitors. Treatments used up to 9 months prior to the first odevixibat dose are to be collected (including the dose). If prior medications are discontinued, the date of discontinuation is to be provided. If the prior medication involves other IBAT inhibitors, any adverse events leading to their discontinuation will be documented, including their resolution.
- f Concomitant medications include ALGS and non-ALGS oriented treatments, including but not limited to rifampicin and/or UDCA.
- g Type and dose of to be collected.
- ^h Planned date and indication are to be collected.
- ¹ Includes pruritus and sleep disturbance, if (semi-) objective scoring data are available. For non-naïve participants, the most recent values prior to the first odevixibat dose are to be collected.
- ^j Laboratory parameters include-AST, ALT, ALP, total bilirubin, direct bilirubin, GGT, INR, albumin, creatinine, sodium, platelet count, and serum bile acid levels reported since the prior data collection. At the Baseline visit, historical (the most recent values in the last 9 months prior to the first odevixibat dose) values are also to be provided if available.
- ^k AEs collection begins once the informed consent has been signed and will end 180 days after the last odevixibat dose (unless consent was withdrawn). Special Situations include pregnancy or breastfeeding status and overdose, off-label use, misuse, abuse, occupational exposure, medication error, and lack of effectiveness (Section 9.1.3).

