7.7 Data Analysis

7.7.1 Analyses Population Definitions

Safety Population: all participants who have taken at least one dose of odevixibat following enrolment.

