7.7.2 Statistical and Analytical Methods

A statistical analysis plan (SAP) describing the planned statistical analysis in detail with table, figure, and listing templates will be developed as a separate document.

Analyses will be primarily descriptive.

Descriptive summaries of continuous variables will include the number of observations, mean, standard deviation, median, range, and 95% confidence intervals (CIs) and/or inter-quartile range when appropriate. Descriptive summaries of categorical variables will include frequencies and percentages. Percentages will be based on the number of non-missing observations. Missing data will also be summarized.

Demographic and baseline characteristics of participants will be summarized using descriptive statistics.

The number and relative frequency of participants who prematurely discontinue participation in the study and reasons for discontinuation will be tabulated.

PAGE 33 OF 76

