7.7.2.2 Evaluation of Secondary Endpoints

Safety data, including but not limited to the incidence of FSV deficiencies and their possible sequelae, the incidence of suspected hepatotoxicity requiring interruption of odevixibat treatment and bleeding events (including events requiring emergency department care, hospitalization, or blood transfusion), and growth and development (in the form of change in height and weight from baseline) will be collected, and descriptive statistics will be presented.

Adverse events will be coded according to MedDRA and will be classified by preferred term (PT) and system organ class (SOC). Adverse event listings will be presented by participant, SOC, and PT. All AEs and Special Situations will be included in the participant data listings.

The incidence of all reported AEs, serious and nonserious treatment-related AEs, all SAEs, all nonserious AEs, AEs leading to death, AEs leading to treatment discontinuation, and Special Situations will be tabulated separately. In addition, summary tables for AEs will be presented by severity and drug relationship (investigator-reported causality assessment). In addition, the incidence of all AEs associated with FSV deficiencies, and the incidence of all suspected hepatotoxicity requiring interruption of odevixibat treatment events and bleeding AEs (including events requiring emergency department care, hospitalization, or blood transfusion) will be tabulated.

Signs and symptoms of FSV deficiency will be summarized at each study visit using descriptive statistics. For each sign and symptom, the change from baseline by visit and the last assessment during treatment will be summarized by a shift table.

Change from baseline in growth (i.e. height [cm], weight [kg], body mass index [kg/m²], and corresponding Z-score [standard deviation from P50 standard growth curve]), will be summarized by visit for participants age < 18 using descriptive statistics.

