7.7.3 Subgroup Analyses

Subgroup analyses may be defined in the SAP.

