9.2.1 Collection of AEs/SAEs/Special Situations in the eCRF

The collection and reporting of AEs will follow regulations related to non-interventional studies (NIS).

All AEs, whether they are serious/nonserious or related/unrelated, and all Special Situations should be collected in the eCRF during the study. Adverse events will be assessed based on incidence, severity grade, causality, outcome, action taken, and seriousness.

All AEs will be collected in the eCRF from the signing of the ICF until 180 days after the last dose of odevixibat or until consent is withdrawn.

9.2.2 Reporting of SAEs, Nonserious Adverse Drug Reactions, and Special Situations to Sponsor Pharmacovigilance

Investigators must report to Ipsen Pharmacovigilance all the following events using the electronic data collection tool or the "Adverse Event and Special Situation reporting form for non-interventional studies" (134232-FOR) if the electronic data collection tool is unavailable (Table 2):

- All SAEs: related and non-related
- All related nonserious AEs (adverse drug reactions)
- Any Special Situations (see definitions in Section 9.1.3)

PAGE 44 OF 76

Table 2 Primary Data Collection Non-Interventional Studies

Safety Event	Collected on the eCRF	Reported on the "AE and Special Situation NIS Form" (134232- FOR) to Ipsen Global Pharmacovigilance (if the electronic data collection tool is unavailable)
Nonserious AE	All AEs related or not	Only the related AEs — within 7 calendar days of awareness
SAE	All SAEs related or not	All — within 24 hours of awareness
Pregnancy	All pregnancies	All — within 24 hours of awareness ^a
Special Situations	All Special Situations related or not (regardless of whether associated with an AE)	All (regardless of whether associated with an AE) — within 7 calendar days of awareness

AE=adverse event; eCRF=electronic case report form; NIS=Non-interventional study; SAE=serious adverse event.

All SAEs and pregnancies will be recorded and reported to the sponsor or designee immediately and under no circumstance should this exceed 24 hours (once known), as indicated below. The investigator will submit any updated SAE and pregnancy data to the sponsor within 24 hours of it being available.

All nonserious related AEs and Special Situations (except pregnancy) will be recorded and reported to the sponsor or designee immediately and under no circumstance should this exceed 7 calendar days (once known), as indicated below.

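### Adverse events on odevixibat before consent are not collected for participants already on treatment, so the pooled crude incidences are not incidences since treatment start and will understate new starters' risk if risk is concentrated early

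*Protocol*

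**What the plan says.** Four parts of the protocol bear on this.

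- **Collection window.** Table 1, footnote k: "AEs collection begins once the informed consent has been signed and will end 180 days after the last odevixibat dose". Section 9.2.1 repeats it: "All AEs will be collected in the eCRF from the signing of the ICF until 180 days after the last dose of odevixibat". Section 7.3.2.6 also starts safety data at the signing of consent.
- **Who may enter.** Section 7.2.1 requires a participant to be "On (or starting) active odevixibat treatment". Section 7.1 adds: "Participants who started odevixibat treatment before the implementation of the registry-based study may also be enrolled".
- **Analysis set.** Section 7.7.1 defines only a Safety Population: "all participants who have taken at least one dose of odevixibat following enrolment".
- **Analysis.** Section 7.7.2.2 tabulates "The incidence of all reported AEs, serious and nonserious treatment-related AEs, all SAEs, all nonserious AEs, AEs leading to death" and further AE categories, including suspected hepatotoxicity requiring interruption and bleeding. Under Section 7.7.2, "Descriptive summaries of categorical variables will include frequencies and percentages". No person-time denominator and no split by prior exposure is stated. Section 7.7.3 leaves the door open: "Subgroup analyses may be defined in the SAP".

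Section 7.9 names missing routine data and variation between sites as limitations. It does not mention the unobserved time on drug before consent.

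**The concern.** The cohort mixes two kinds of participant. New starters are observed from about their first dose. Those already on treatment are observed only from consent, so their earlier time on drug is left-truncated. They are also selected: to enter they must still be on odevixibat or be restarting it. Someone who had suspected hepatotoxicity, interrupted, resumed and then consented would contribute no event to that endpoint. Someone who stopped for good would not be in the registry at all.

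A crude percentage over the mixture answers a blurred question. It is not the risk since starting the drug, and it need not be the risk that a new starter faces. The AE, hepatotoxicity and bleeding incidences are secondary endpoints of a registry set up to supply real-world safety data, so a reader will want to know which of these the figure estimates.

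**Working it through.** The protocol gives no AE rate, no AE timing and no expected share of participants already on treatment, so there is no planned figure to reproduce. Two checks were made.

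**1. How much time on drug can be unobserved?** Inputs: US authorization on 13 June 2023 (Section 5.3), data collection planned from November 2024 (Section 4), enrolment closing 3 years after the start (Section 7.2.4).

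- 13 June 2023 to 1–30 November 2024: 16.7 to 17.6 months.
- 13 June 2023 to 1–30 November 2027: 52.6 to 53.6 months.

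So exposure since authorization can reach about 17 months at the start of the registry and about 53 months by the close of enrolment, with no AE capture before consent.

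**2. What does pooling do to the incidence?** All hazards and shares here are assumptions. The hazard is *a* per year in the first 6 months on drug and *b* per year afterwards. Follow-up is 2 years from consent, the minimum in Section 7.2.4. Participants already on treatment enter at least 6 months after first dose, and a share *f* of the cohort is already treated.

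- New starter: 1 − exp(−(0.5*a* + 1.5*b*))
- Already treated: 1 − exp(−2*b*)
- Pooled: (1 − *f*) × new starter + *f* × already treated

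For the falling hazard (*a* = 0.40, *b* = 0.10):

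- New starter: 1 − exp(−0.35) = 29.5%
- Already treated: 1 − exp(−0.20) = 18.1%
- Pooled at *f* = 0.5: 0.5 × 29.5 + 0.5 × 18.1 = 23.8%

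| Hazard, *a* then *b* | New starter | Already treated | Pooled, *f* = 25 / 50 / 75% | Pooled minus new starter, points |
|---|---|---|---|---|
| Falling, 0.40 then 0.10 | 29.5% | 18.1% | 26.7 / 23.8 / 21.0% | −2.8 / −5.7 / −8.5 |
| Constant, 0.15 | 25.9% | 25.9% | 25.9 / 25.9 / 25.9% | 0 |
| Rising, 0.05 then 0.20 | 27.7% | 33.0% | 29.1 / 30.4 / 31.7% | +1.3 / +2.6 / +3.9 |

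With 45 participants, the falling case means 13.3 expected participants with an event if all were new starters, against 12.0 / 10.7 / 9.4 in the mixture.

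If the percentage is instead read as incidence from each participant's own first dose, it is too low in every case, because the events before consent are absent. With 1.5 years of earlier exposure and *f* = 50%, the incidence since first dose averages the new starters' 2-year figure and the already-treated group's 3.5-year figure, 1 − exp(−(0.5*a* + 3*b*)):

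- Falling: (29.5 + 39.3)/2 = 34.4%, against 23.8% pooled.
- Constant: (25.9 + 40.8)/2 = 33.4%, against 25.9%.
- Rising: (27.7 + 46.5)/2 = 37.1%, against 30.4%.

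The model leaves out the exclusion of people permanently off drug before consent. That selection would tend to lower the already-treated group's figure further.

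**The case against.** The strongest reply is that stratified tables and exposure-adjusted rates are ordinary SAP content. Section 7.7.2 sends the detail there, Section 7.7.3 allows subgroups, and the SAP is not at hand. It is right that the protocol does not require pooled-only reporting, and a missing subgroup table would be no finding by itself. What stands against the reply is that the protocol itself fixes the collection window, the mixed entry, the single population and the crude percentage, and that Section 7.9 does not declare the consequence. A SAP can split the table, but it cannot recover AEs that were never collected.

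A reader might infer that the pooled incidences are simply biased downward. The documents do not support that. Compared with the first two years on drug, the direction depends on how the hazard changes with time on drug, as the table above shows, and the protocol says nothing about that. Nor does it present its AE incidences as risk since first dose; it speaks of participants on chronic treatment.

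Three further points are fair:

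- Starting AE collection at consent is not an error in itself, since Section 7.2.1 requires consent before study data are collected.
- Stopping before consent does not always bar entry. A person who restarts is eligible, and only those permanently off drug are lost.
- The baseline visit takes general medical history, fat-soluble vitamin levels and the vitamin deficiency questionnaire, and, if available, treatment dates and reasons for dose changes (Sections 7.2.7.1 and 7.3.2.8). Some earlier trouble will be visible there, though not as AEs, so the point is weaker for vitamin deficiency than for hepatotoxicity or bleeding.

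Finally, sampling error is large at this size. Exact 95% intervals are 7.7 to 38.6% for 6/30 and 9.6 to 34.6% for 9/45, wider than any shift in the illustration. That limits what any table can show, but it does not make the mixed percentage easier to interpret.

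**Conclusion.** The point holds in conditional form. Events on odevixibat before consent are not collected as AEs for participants already on treatment, and people permanently off the drug by then are absent. The pooled crude incidences of AEs, suspected hepatotoxicity requiring interruption and bleeding therefore do not represent incidence since treatment start. They will understate the risk for new starters if risk is concentrated early.

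The size cannot be fixed from the protocol. The shifts of about −8.5 to +4 points against new starters rest entirely on the assumed hazards, the assumed shares of 25 to 75% and two years of follow-up. They show how direction and size depend on those assumptions and are not an estimate for this registry.

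**What to change.** - **Section 7.7.2.2:** keep the overall table and add the incidences of AEs, suspected hepatotoxicity requiring interruption and bleeding separately for participants starting odevixibat at or after enrolment and for those already on treatment. Give exposure-adjusted rates whose person-time begins at consent.
- **Interpretation:** base any statement about early risk on the new starters only.
- **Section 7.9:** state that time on drug before consent is unobserved for AEs and that participants already on treatment are selected for continuing it.

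The odevixibat start date is already recorded (Sections 7.2.7.1 and 7.3.2.8) and the consent date must be in the source documents (Section 7.8.3), so this is text and table work.

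The cost is precision. With 30 participants split evenly, 3/15 = 20% has an exact 95% interval of 4.3 to 48.1%, against 7.7 to 38.6% for 6/30. That is why the overall table should stay beside the split.

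An optional further step is to record, at baseline, AEs on odevixibat before consent. The protocol already looks back in this way for AEs that led to stopping other drugs of the same class (Section 7.3.2.2). This would need a change to the case report form, and recall would be incomplete.

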7.2.8 Study Discontinuation/Withdrawal

The participant can withdraw (or be withdrawn if the participant is a child upon legal representative's decision) from this registry-based study at any time. The date and primary reason for withdrawal should be recorded in the eCRF as well as if the participant stopped odevixibat or not.

For study results to remain unbiased, it is important that no data are modified; as a result, the data collected in clinical studies need to remain untouched for results to be trusted. Should the participant withdraw from the study, no further data will be collected; nevertheless, data collected up to the time of the withdrawal will be kept for analysis, safety, and integrity of study results.

PAGE 28 OF 76

The participant will be withdrawn from the registry-based study if:

- They enroll in any interventional clinical trial
- The participant is no longer receiving odevixibat and has completed the last follow-up visit up to 180 days after last dose of odevixibat (see Section 9.4 for follow-up of AEs and Section 9.1.3.1 for follow-up of pregnancies)

Note: Participants can remain in the registry-based study during odevixibat treatment interruptions.

Investigators may decide to stop their participant's participation in the study at any time without consequences on the normal participant follow-up.

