- ¹ The fat-soluble vitamin deficiency questionnaire will be included in the eCRF and completed by the investigator (Section 7.6.1).

PAGE 26 OF 76

7.2.7 *Study Visit(s)*

Visits will be done in accordance with routine clinical practice (Follow-up Visits are expected to occur at least every 6 months or more frequently, based on the investigator's judgement). Investigators are encouraged to contact the participants (e.g., text-based reminders or phone calls to caregivers) to ensure follow-up visits are attended and to facilitate rescheduling, if necessary.

The registry-based study will assess data collected at the Baseline Visit and Follow-up Visits.

The End of Study for participants will be the last Follow-up Visit as per routine clinical practice performed before the planned end of data collection (approximately 5 years after the start of data collection, see Section 4), withdrawal of consent, lost-to follow up, or 180 days after treatment discontinuation, whichever comes first.

7.2.7.1 *Baseline*

Investigators at participating sites will identify participants who fulfil the inclusion and none of the exclusion criteria. Signed informed consent should be obtained prior to enrolment based on local regulations, and once inclusion and exclusion criteria have been satisfied. If the participant is < 18 years old (or the legal age of consent in the jurisdiction in which the study is taking place), assent and parent or legally authorized representative consent will also be required.

For this registry-based study, the following variables will be captured from Baseline Visit records as available:

- Age, sex, weight, height, ALGS genetic variant, date of birth (MM/YYYY), and date
 of ALGS diagnosis
- General medical or surgical history
- Prior surgical procedures related to ALGS, including but not limited to prior biliary diversion surgery (date and type of surgery) and liver transplantation (date and donor information)
- Prior medications
 - Prior medications refer only to medications related to the treatment of ALGS, including but not limited to rifampicin, UDCA, and/or other IBAT inhibitors, taken up to 9 months prior to the first odevixibat dose
- Concomitant medications
 - Concomitant medications include ALGS and non-ALGS oriented treatments, including but not limited to rifampicin and UDCA
- Concomitant vitamin supplementation
- Odevixibat treatment dose and start date

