7.3.1.1 Primary Endpoints

- Incidence of biliary diversion surgery, liver transplantation, or death in participants with ALGS chronically treated with odevixibat.
- Surgical biliary diversion-free survival, defined as time from the start of odevixibat treatment to the first occurrence of surgical biliary diversion or death.
- Liver transplant-free survival, defined as time from the start of odevixibat treatment to the first occurrence of liver transplant or death.
- Overall survival, defined as time from the start of odevixibat treatment to death.

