7.5 Study Size

No formal sample size calculations have been performed for this registry-based study.

Enrolment will be based on the number of participants prescribed odevixibat and their willingness to participate in the study, but the goal will be to enroll approximately 30 to 45 participants with ALGS.

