7.7.2.1 Evaluation of Primary Endpoint

The incidence of biliary diversion surgery, liver transplantation, or death will be assessed using descriptive statistics. Depending on the data available, event free survival endpoints will be summarized using the Kaplan-Meier method. Median time to event with 2-sided 95% CIs and the first and third quartiles will be reported. Survival curves will be presented as well. In addition, survival probability estimates at 6 months, 12 months, and then every 6 months and the associated 2-sided 95% CIs will be reported.

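### After an investigator-decided stop or a loss to follow-up, the registry does not ask for diversion, transplant or vital status, although consent may still stand and routine care may continue

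*Protocol*

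**What the plan says.** Section 7.2.8 of the protocol gives investigators an open right to end participation: "Investigators may decide to stop their participant's participation in the study at any time without consequences on the normal participant follow-up". No criteria and no closing data item are attached.

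Loss to follow-up is a separate exit. Table 1 footnote b and Section 7.2.7 define the end of study as the last routine visit before the planned end of data collection, "withdrawal of consent, lost-to follow up, or 180 days after treatment discontinuation, whichever comes first".

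For withdrawal, Section 7.2.8 asks for this: "The date and primary reason for withdrawal should be recorded in the eCRF as well as if the participant stopped odevixibat or not". For a participant who withdraws, it adds: "Should the participant withdraw from the study, no further data will be collected". A closing visit is recommended only after treatment discontinuation (Table 1 footnote b).

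The primary endpoints in Section 7.3.1.1 open with "Incidence of biliary diversion surgery, liver transplantation, or death in participants with ALGS chronically treated with odevixibat". They continue with three time-to-event measures, for example "Liver transplant-free survival, defined as time from the start of odevixibat treatment to the first occurrence of liver transplant or death". Under Section 7.7.2.1 the incidence is described and, depending on the data available, "event free survival endpoints will be summarized using the Kaplan-Meier method".

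**The concern.** The primary results depend entirely on knowing who had a diversion, a transplant or died, and when. An investigator who stops participation knows the clinical course. A family lost to the site may have moved to a transplant centre. Either exit could therefore go with a worse outlook. The investigator clause itself presumes that ordinary care goes on, so the record that shows the event may sit at the same clinic while the registry no longer reads it.

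Kaplan-Meier estimation treats a censored participant as having the same future risk as those still observed. If that fails in the adverse direction, the curves look too good. The crude incidence is also too low if such participants are counted as event-free. Whether status is collected after exit is a matter for the protocol: an analysis plan can only choose how to treat an unknown.

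**Working it through.** **What is collected after each exit.** The sections, side by side:

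| Situation | What the protocol provides |
|---|---|
| Up to the last attended visit | Diversion, transplant and death with dates (Table 1, Section 7.2.7.2) |
| Treatment discontinued | Follow-up to 180 days, closing visit recommended (Section 7.2.9, Table 1 footnote b) |
| Investigator stop, consent stands | No outcome check stated |
| Loss to follow-up, consent stands | No outcome check stated |
| Adverse events | Collected until 180 days past the final dose or consent withdrawal (Section 9.2.1). An investigator stop is not named as an end |
| Procedures | Not adverse events; the underlying condition is (Section 9.1.1) |

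So a fatal serious adverse event could at most still be reportable under Section 9.2.1. A later diversion or transplant would not be captured as such. Sections 7.1 and 7.2.4 do not list investigator decision or loss to follow-up among the ends of participation. Sections 7.2.9 and 9.2.1 do not fit a stop under 7.2.8 while consent stands.

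**Size: no figure to reproduce.** The protocol makes no sample size calculation and states no dropout rate. On numbers it says only "the goal will be to enroll approximately 30 to 45 participants with ALGS". The rest is illustration.

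*Step 1, crude incidence.* One missed event, with the participant kept in the denominator as event-free, lowers incidence by 1/N: 1/30 = 3.3 points, 1/45 = 2.2 points. The inputs below are assumed cumulative incidences near 15% and 25%, borrowed from the childhood transplant range in Section 5.2, which is not a rate over the study period.

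| N | Events, complete | Two missed |
|---|---|---|
| 30 | 4 (13.3%, 95% CI 3.8 to 30.7) | 2 (6.7%, 0.8 to 22.1) |
| 30 | 8 (26.7%, 12.3 to 45.9) | 6 (20.0%, 7.7 to 38.6) |
| 45 | 7 (15.6%, 6.5 to 29.5) | 5 (11.1%, 3.7 to 24.1) |
| 45 | 11 (24.4%, 12.9 to 39.5) | 9 (20.0%, 9.6 to 34.6) |

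Intervals are Clopper-Pearson. If k participants have unknown status, the span from best to worst case is k/N. For k = 3 this is 10 points (N = 30) or 6.7 points (N = 45).

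*Step 2, Kaplan-Meier.* Simulation with uniform enrolment over 3 years, cut-off at 5 years, exponential event times counted from enrolment for simplicity, and 3,000 runs per setting. A share s of would-be events is censored up to 6 months beforehand. Mean estimated 2-year risk, nearly the same for N = 30 and N = 45:

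| Assumed true risk | s = 0 | 10% | 20% | 30% | 40% |
|---|---|---|---|---|---|
| 0.15 | 0.15 | 0.135 | 0.12 | 0.11 | 0.09 |
| 0.25 | 0.25 | 0.23 | 0.21 | 0.18 | 0.16 |

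Both the true risk and s are assumptions.

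*Step 3, how many transplants might fall after exit.* Spread 15% to 25% evenly over 18 years of childhood: −ln(0.85)/18 = 0.0090 and −ln(0.75)/18 = 0.0160 per year. With an assumed mean follow-up of 3.5 years, 30 × 3.5 × 0.0090 = 0.95 and 45 × 3.5 × 0.0160 = 2.5 expected transplants. Assume the two exits together occur at 5% or 10% per year, follow-up is uniform on 2 to 5 years, and risk after exit is 1 or 3 times the risk before. Expected transplants after exit are then about 0.1 to 0.6 at 5% per year and 0.15 to 1.1 at 10% per year. At a multiplier of 1 the censoring is non-informative and Kaplan-Meier is not biased.

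**The case against.** Several points on the other side are sound.

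- A reader might infer that the registry makes no last check of status at all. It does collect the three outcomes up to the last attended visit. Only later events are at issue.
- A reader might take the sentence on collecting no further data as covering investigator stops. It is written for participant withdrawal. For investigator stops the protocol is silent or, through Section 9.2.1, inconsistent.
- A reader might infer that investigators may remove participants for any reason. Section 7.2.8 says when they may do so and is silent on reasons; the any-reason wording belongs to the sponsor's termination right in Section 7.2.10.
- Deleting the investigator clause is not clearly right. Section 7.13 requires renewed consent after substantial amendments and at legal age, and the clause may be the exit route for someone who does not re-consent.
- The primary reason for withdrawal is already recorded, and reasons for discontinuation are tabulated (Sections 7.2.8 and 7.7.2). A sensitivity analysis belongs in the analysis plan and is not missing here.
- The study is descriptive, without formal testing (Section 7.9), and nothing shows that such exits will be frequent or related to prognosis.

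The gap remains. Encouraged contact (Section 7.2.7) and monitor calls to limit dropout (Section 7.8.1) aim at attendance and do not establish outcomes after an exit. Section 7.9 admits missing data for assessments that are not routinely done, which is a different matter from losing primary events.

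**Conclusion.** The concern holds in a limited form. After an investigator-decided stop or a loss to follow-up with consent intact, the protocol does not ask for diversion, transplant or vital status, and these outcomes are the primary endpoints. If the exits go with worse prognosis, incidence and event-free survival would both look too favourable.

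The size is conditional. The 3.3 or 2.2 points per missed event follow from N alone, given that the participant is counted as event-free; Section 7.7.2.1 does not say how exits are counted. Every Kaplan-Meier figure and every expected count rests on exit rates, risks and multipliers that the protocol does not give. A reader might infer that bias is established. The documents show only that it is possible, and that it could not be corrected afterwards. This is a cheap improvement to data collection in a small registry where few events can be expected.

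**What to change.** Keep the investigator clause and add to Section 7.2.8:

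> For exits by investigator decision or loss to follow-up where consent has not been withdrawn or lapsed, the site records biliary diversion, liver transplant and vital status with dates, from the medical record or a call where possible, at exit and at the end of data collection.

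Reconcile Sections 7.1, 7.2.4, 7.2.7, 7.2.8, 7.2.9 and 9.2.1 on what ends participation and what ends data collection.

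The cost is one sentence, a short status form, and a chart check or call for a few participants. It adds no test or procedure, so it fits the observational design. Status may stay unknown for some of those lost to follow-up, since contact has failed and the chart may hold nothing later.
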